9.2.3.1. Partial Date Imputation

The following table shows partial date imputation for some special cases.

Table 9.3.2.1. Partial Date Imputation in Some Special Cases

Type of Date/Time	Day is missing	Month is missing	Both Month and Day are missing
concomitant medication start date	the day of treatment start date ¹ if medication occurs in the same month and the same year as the subject's in treatment start date, otherwise, the first day of month	the month of treatment start date if medication occurs in same year as the in-treatment start date, otherwise, the first month of year	treatment start date if medication occurs in the same year as the in-treatment start date, otherwise, no imputation
concomitant medication end date	day of study end date if medication occurs in the same year and the same month as the subject's in-study end date, otherwise, last day of month	month of study end date if medication occurs in the same year as the subject's in-study end date, otherwise, December	treatment end date if medication occurs in the same year as the subject's in-study end date, otherwise, considered ongoing
medical history or prior medication start date	first day of month	first month of year	study start date if it occurs in the same year as the one in study start date, otherwise, January 1
end date for medical history or prior medication	day of study end date if it occurs in the same year and the same month as ones in study end date, otherwise, last day of month	month of study end date if it occurs in same year as one in study end date, otherwise, December	study end date if it occurs in the same year as one in study end date, otherwise, December 31

[1] Treatment start date: date of procedure or device implantation

Table 8.3.2.1. Partial Date Imputation in Some Cases (continued)

Type of Dates	Day is missing	Month is missing	Both Month and Day are missing
AE start date	day of treatment start date ¹ if AE occurs in the same year and same month as ones in treatment start date, otherwise, last day of month	month of treatment start date if AE occurs in the same year as one in treatment start date, otherwise, January	treatment start date if AE occurs in the same year as treatment start date, otherwise, as January 1
AE end date	same day as study end date if AE occurs in the same year and the same month as study end date, otherwise, last day of month	same month of study end date if AE occurs in the same year as one in study end date, otherwise, December	study end date if AE occurs in the same year as one in study end date, otherwise, December 31

[1] Treatment start date: date of procedure

9.2.4. Interim Analysis

No interim analysis is planned for this study.

9.2.5. Multicenter Studies

There are up to 15 sites enrolling 200 subjects in the single arm study, data across all sites will be pooled to perform all primary and secondary analyses. No stratification analysis by sites will be performed.

9.2.6. Multiple Comparisons/Multiplicity

This is a prospective, multi-center, single-arm study. No comparisons will be performed. Therefore, no multiple comparisons or multiplicity will be conducted.

9.2.7. Use of an Efficacy Subset of Patients

It is not applicable to this study.

9.2.8. Active Control Studies Intended to Show Equivalence

It is not applicable to this study.

9.2.9. Examination of Subgroups

Primary endpoint will be analyzed by reasons for use of Scoreflex NC device.

9.2.10. Analysis Windows and Definitions

Analysis windows and definitions are not applicable as the subjects are complete at discharge. No follow up is conducted for this protocol.

9.3. Patient Disposition, Demographics and Other Baseline Characteristics

A tabulation of subject disposition will be presented including the number enrolled, the number of patients who received procedure, the number of major protocol violators, number of patients with available data of the primary endpoint, and the number of withdrawals, including reasons for withdrawal as documented on the CRF.

Baseline demographic characteristics will be summarized for ITT population. Other baseline characteristics will be reported as well.

9.3.1. Listing of Individual Data

A by-subject listing of demographic, endpoint event as well as angiographic core lab data will be provided.

9.4. Primary Endpoint Analysis

The primary endpoint is a device procedural success endpoint based on a composite of the following components:

- Successful delivery, inflation, deflation, and withdrawal of the study balloon
- No evidence of vessel perforation, flow limiting dissection (grade C or higher) or reduction in TIMI flow from baseline as related to the Scoreflex NC study balloon
- Final TIMI flow grade of 3 at the conclusion of the PCI Procedure

A patient's procedure is considered a success if all of three components are successful.

Number and percentages of each component above and the overall composite primary endpoint will be calculated and presented, by both patient level and lesion level, with two-sided 95% confidence intervals at index procedure, based on the Intent-to-Treat (ITT) and Per-Protocol (PP) population, respectively.

Because this study is a prospective, open label, multi-center, single arm, observation study, no formal hypothesis testing will be performed.

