### 5.2 Target Lesion

- Lesion that is to be treated with the Scoreflex NC study device during the index procedure.
- Target lesions (maximum of 2) may be located in the same or different coronary arteries.
- Target lesion composed of multiple focal lesions that can be covered with one stent will be considered as a single lesion.
  - *Note:* A separate Scoreflex NC study catheter must be used for treatment of each target lesion, if there is more than one target lesion identified to be treated.

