6.2.1. Primary Safety and Efficacy Endpoint

The primary endpoint is a successful procedure based on the following composite components on a per-patient level:

- Successful delivery, inflation, deflation, and withdrawal of the study balloon
- No evidence of vessel perforation, flow limiting dissection (grade C or higher) or reduction in TIMI flow from baseline as related to the Scoreflex NC study balloon
- Final TIMI flow grade of 3 at the conclusion of the PCI Procedure

A patient's procedure is considered a success if all three components are achieved.

Each component of the primary endpoint measures will be reported as individual components as well..

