9.2. General Considerations

9.2.1. General Methods

All descriptive statistical analyses will be performed using SAS (Version 9.4 or higher), unless otherwise noted. Derived variables will be programmed by the study programmer/statistician, and then verified by an independent programmer/statistician (e.g., age or height conversions). The program review also will include a check whether analyses conform to specifications of the SAP. All output will be incorporated into Microsoft Word files and formatted as to the appropriate page size(s).

All primary and secondary endpoints will be evaluated using descriptive statistics only. No hypothesis tests will be performed.

Statistics for continuous outcomes will include N, mean, median, standard deviation, minimum, and maximum. Binary outcomes will be summarized using frequencies, percentages and two-sided exact 95% confidence intervals for the primary and secondary endpoints. For categorical variables, the number and percentage within each category of the parameter will be calculated.

The baseline demographic and clinical characteristics, lesion characteristics, procedure information will be summarized by descriptive statistics for the ITT population.

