13. STATISTICAL TABLES TO BE GENERATED

- Table 1. Patient Disposition -ITT Population
- Table 2. Demographics and Clinical Characteristics -ITT Population
- Table 3. Baseline Patient Medical History - ITT Population
- Table 4. Baseline Patient Laboratory Value -ITT Population
- Table 5. Baseline Patient Medications -ITT Population
- Table 6. Procedure -Per Patient -ITT Population
- Table 7. Lesion Characteristics (Lesion based) -ITT Population
- Table 8. Scoreflex NC Device Usage (Lesion based) -ITT Population
- Table 9. Protocol Deviations -ITT Population
- Table 10.1.1. Summary of Primary Endpoint Analysis by Subcomponents at Patient Level -ITT Population
- Table 10.1.2. Summary of Primary Endpoint Analysis by Subcomponents at Lesion Level -ITT Population
- Table 10.2.1. Summary of Primary Endpoint Analysis by Subcomponents at Patient Level -PP Population
- Table 10.2.2. Summary of Primary Endpoint Analysis by Subcomponents at Lesion Level -PP Population
- Table 11.1. Summary of Secondary Endpoint Analysis at Patient Level -ITT Population
- Table 11.2. Summary of Secondary Endpoint Analysis at Patient Level -PP Population
- Table 12. Summary of Primary Endpoint Analysis by Reason for use of Scoreflex NC at Patient Level -ITT Population
- Table 13.1 Summary of Adverse Events -ITT Population
- Table 13.2 Summary of Relatedness of MACE to the Procedure and the Device -ITT Population
- Table 14.1 Baseline Angiographic Findings -ITT Population
- Table 14.2 Quantitative Angiographic Findings -ITT Population
- Table 14.3 Post Coronary Dilatation Catheter Morphology -ITT Population
- Table 14.4 Final Post-Procedure Morphology -ITT Population

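### SAP 9.4 plans lesion-level 95% intervals that ignore pairing of two target lesions in one patient; under positive correlation they are somewhat too narrow (minor)

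*SAP*

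**What the plan says.** The endpoint is defined per patient. SAP 6.2.1 states: "The primary endpoint is a successful procedure based on the following composite components on a per-patient level". Protocol section 6 also assesses device success per patient.

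SAP 9.4 adds a second unit of analysis, presenting the composite and its components "by both patient level and lesion level, with two-sided 95% confidence intervals at index procedure". The outputs in SAP 13 are "Table 10.1.2. Summary of Primary Endpoint Analysis by Subcomponents at Lesion Level -ITT Population" and "Table 10.2.2. Summary of Primary Endpoint Analysis by Subcomponents at Lesion Level -PP Population".

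The interval type comes from SAP 9.2.1: "Binary outcomes will be summarized using frequencies, percentages and two-sided exact 95% confidence intervals for the primary and secondary endpoints".

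Protocol 5.2 lets one patient supply two lesions: "Target lesions (maximum of 2) may be located in the same or different coronary arteries". It also requires: "A separate Scoreflex NC study catheter must be used for treatment of each target lesion".

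The secondary endpoints are tabulated by patient, for example "Table 11.1. Summary of Secondary Endpoint Analysis at Patient Level -ITT Population".

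No section of the available text mentions within-patient correlation or a clustered interval. SAP 9.2.2 rules out covariate adjustment and SAP 9.2.5 rules out stratification by site; neither addresses paired lesions.

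**The concern.** An exact binomial interval on a lesion count assumes that lesions succeed or fail independently. Two target lesions in one patient share the patient, the operator, the session and possibly the artery, so some positive correlation is plausible. If it exists, the count varies more than the binomial model allows and the interval is too short.

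At stake is how Tables 10.1.2 and 10.2.2 are read. The study tests nothing, so estimates and intervals are its whole inferential output. The lesion-level interval will look tighter than the per-patient one beside it, and the text does not require the number of two-target-lesion patients to be shown there.

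**Working it through.** **No planned figure to reproduce.** SAP 9.1 gives 200 patients without a precision target or hypothesis. The only benchmark is the nominal 95%. With one lesion per patient (n = 200), the exact interval covers 96.8% on average for true success p from 0.90 to 0.99. Exact intervals therefore start with some slack.

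**Inputs from the documents:** 200 patients; at most two target lesions each; two-sided exact 95% intervals.

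**Assumed, because the documents do not give them:**
- f, the share of patients with two target lesions: 5% to 50%.
- ICC, the within-patient correlation of lesion success: 0 to 0.5.
- p, the true success rate: averaged over 0.90–0.975 and, separately, over 0.90–0.99. The predecessor device's 94.8% procedural success (Protocol 2.6.1) lies in both ranges.

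**Step 1: coverage of the unadjusted interval.** The number of successes is the sum of 200(1 − f) single lesions and 200f pairs, where P(both succeed) = p² + ICC·p(1 − p). Its distribution is computed exactly. The interval is the exact binomial one on 200(1 + f) lesions. Average coverage in %, over p = 0.90–0.975 / 0.90–0.99:

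| f | ICC 0 | ICC 0.3 | ICC 0.5 |
|---|---|---|---|
| 5% | 96.5 / 96.7 | 96.2 / 96.5 | 96.1 / 96.3 |
| 10% | 96.4 / 96.7 | 95.9 / 96.2 | 95.6 / 95.9 |
| 20% | 96.4 / 96.6 | 95.5 / 95.7 | 94.8 / 95.1 |
| 30% | 96.3 / 96.5 | 95.0 / 95.3 | 94.0 / 94.4 |
| 50% | 96.3 / 96.4 | 94.3 / 94.5 | 92.9 / 93.2 |

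The point at which the average crosses 95% depends on the range of p. Over p = 0.90–0.99, f = 20% needs an ICC of about 0.53. Over p = 0.80–0.95 it needs about 0.31, and f = 10% needs about 0.61. No single threshold should be quoted.

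**Step 2: size of the change in the interval.** Design effect D = 1 + ICC·2f/(1 + f). The clustered interval is the exact formula with successes and lesions both divided by D. At 95% observed success:

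| Lesions | ICC | D | Effective lesions | 95% interval (%) |
|---|---|---|---|---|
| 228/240 (f = 20%) | unadjusted | 1 | 240 | 91.43–97.39 |
| | 0.3 | 1.100 | 218.2 | 91.21–97.49 |
| | 0.5 | 1.167 | 205.7 | 91.07–97.55 |
| 285/300 (f = 50%) | unadjusted | 1 | 300 | 91.89–97.17 |
| | 0.3 | 1.200 | 250.0 | 91.52–97.35 |
| | 0.5 | 1.333 | 225.0 | 91.28–97.46 |

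The lower limit falls by 91.43 − 91.21 = 0.22 or 91.43 − 91.07 = 0.36 point at f = 20%, and by 91.89 − 91.52 = 0.37 or 91.89 − 91.28 = 0.61 point at f = 50%.

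**Step 3: how much of the apparent gain is real.** The per-patient lower limit for 190/200 is 91.00. At f = 20% the unadjusted gain is 91.43 − 91.00 = 0.43 point. At ICC 0.3, 91.21 − 91.00 = 0.21 point survives, about half; at ICC 0.5, 0.07 point survives.

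**Step 4: does the proposed interval work when D must be estimated?** The ICC is estimated over the pairs as the mean of (y₁ − p̂)(y₂ − p̂), divided by p̂(1 − p̂), and truncated to 0–1. The patient count serves as effective sample size if no lesion fails. In 20,000 simulated trials at each of 31 values of p from 0.90 to 0.975, average coverage was 96.3% (ICC 0.3) and 96.0% (ICC 0.5) at f = 20%, and 96.0% and 95.9% at f = 50%. The lowest value at any single p was 94.8% (f = 50%, ICC 0.5).

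**The case against.** The strongest reply is that this changes nothing of substance. SAP 6.2 defines no hypothesis, there is no performance goal, the endpoint is per patient, and Tables 10.1.1 and 10.2.1 give the patient-level results alongside. At f = 20% the correction is below 0.4 point. That stands, and it sets the severity.

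High values of f also have no anchor. Only two lesions may be treated and one may be a non-target lesion, so a two-lesion patient need not supply two target lesions. The nearest figure is the predecessor catheter's first-in-man registry (Protocol 2.6.1): 37 lesions in 30 subjects, which is 7/30 = 23% if nobody had more than two. That is a small single-centre analogy, but it suggests weight on the middle rows of the table. Separate catheters for each target lesion also make full correlation unlikely.

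The clustered interval rests on little information. At f = 20% and p = 0.95, about 80 × 0.05 = 4 paired lesions are expected to fail. At ICC 0.3 the truncated estimate was zero in about 36% of simulated trials. The estimate is poor, but Step 4 shows that average coverage still holds.

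The table shells, whose update SAP 12 logs for version 2.0, are not in the available text and might carry a footnote.

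A reader might infer more: that these intervals will under-cover in this trial, that the extra precision is wholly spurious, or that the primary or secondary results are affected. The documents support none of this. They give neither f nor the ICC, extra lesions carry real information whenever the ICC is below 1, and the primary and secondary results are also tabulated by patient.

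**Conclusion.** The gap is real and minor. As written, the plan puts an independence-based interval on data that may be paired, and with positive correlation that interval is too narrow. Whether average coverage falls below 95% depends on quantities the documents do not give. It does not at f of 10% or less with ICC up to 0.5, it is borderline at f = 20% with ICC 0.5, and it does at f = 50% with ICC 0.3 or more.

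The figures assume 200 patients and the exact method of SAP 9.2.1, since SAP 9.4 does not itself name the method. A simple normal-approximation interval would average only 92.4% over p = 0.90–0.99 even without clustering. PP figures would differ slightly with fewer patients. The point is confined to Tables 10.1.2 and 10.2.2. How a patient with one failed and one successful target lesion is scored at patient level is a separate question.

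**What to change.** Add to SAP 9.4 that lesion-level intervals account for clustering of lesions within patients, and name the method. One suitable choice is an exact interval on the number of lesions divided by the estimated design effect, with the patient count as effective sample size if no lesion failed. Footnote Tables 10.1.2 and 10.2.2 with the method and the number of patients contributing two target lesions.

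The cost is a sentence, a footnote and modest programming, because the ICC is estimated separately for the composite and each component in two tables. No new data are needed and the patient-level results do not change. The lesion-level intervals become slightly wider, and the ICC estimate will be imprecise when few paired lesions fail. The no-failure fallback is conservative and should be labelled so: with 240 of 240 successes the lower limit is 0.025^(1/200) = 98.2% instead of 0.025^(1/240) = 98.5%. It would rarely apply; with 240 independent lesions at p = 0.975 the chance of no failure is 0.975^240, about 0.2%.

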9.5. Secondary Endpoint Analyses

The secondary endpoints consist of angiographic procedural efficacy, clinical, and peri-procedural endpoints.

Binary secondary endpoint will be summarized using frequency, percentage, and two sided exact 95% confidence interval through hospital discharge based on the Intent-to-Treat (ITT) and Per-Protocol (PP) population, respectively.

For the continuous binary endpoint, i.e. Improvement in Minimum Lumen Diameter, the simple statistic description such as mean, median, and standard deviation will be presented.

9.6. Concomitant Medications and Medical History

The medical history and concomitant medication will be summarized in the subject demographic and discharge data.

9.7. Adverse Events

For adverse event (AE) analyses, summary tables and detailed patient listings will be provided for all major adverse cardiac events (MACE). Adverse Events will be summarized by relationship to the procedure, to the study device, and by seriousness. MACE will be reported on a per-patient level as a percent (%) of subjects whom experience at least one MACE. If a patient has more than one MACE, only one of MACEs will be used to calculate to percent of subjects who experienced at least one event. Except where indicated, a subject reporting the same MACE more than once will be counted once when calculating the number and percentage of subjects with that particular event.

A listing for MACE will be provided. All safety analyses will be based on the ITT Population.

9.8. Supportive Analyses

Additional analyses may be performed per sponsor's requests.

10. CHANGES TO ANALYSES PLANNED IN THE PROTOCOL

There were no changes to the analyses planned in the protocol.

12. CHANGES TO THE STATISTICAL ANALYSIS PLAN

Any changes to the planned statistical analyses made prior to the analysis of the primary endpoints will be documented in an amended SAP, which will be approved prior to performing the analyses. Any unanticipated changes from the planned statistical methods after analyzing the primary endpoint data will be documented in the clinical study report with a reason for the deviation.

Version/Date	Page(s)	Old Version	New Version	Reason for change
1.0/13JAN2020	N/A	N/A	N/A	
2.0/28MAY2020	25	1.0	2.0	Shell updates

13. STATISTICAL TABLES TO BE GENERATED

- Table 1. Patient Disposition -ITT Population
- Table 2. Demographics and Clinical Characteristics -ITT Population
- Table 3. Baseline Patient Medical History - ITT Population
- Table 4. Baseline Patient Laboratory Value -ITT Population
- Table 5. Baseline Patient Medications -ITT Population
- Table 6. Procedure -Per Patient -ITT Population
- Table 7. Lesion Characteristics (Lesion based) -ITT Population
- Table 8. Scoreflex NC Device Usage (Lesion based) -ITT Population
- Table 9. Protocol Deviations -ITT Population
- Table 10.1.1. Summary of Primary Endpoint Analysis by Subcomponents at Patient Level -ITT Population
- Table 10.1.2. Summary of Primary Endpoint Analysis by Subcomponents at Lesion Level -ITT Population
- Table 10.2.1. Summary of Primary Endpoint Analysis by Subcomponents at Patient Level -PP Population
- Table 10.2.2. Summary of Primary Endpoint Analysis by Subcomponents at Lesion Level -PP Population
- Table 11.1. Summary of Secondary Endpoint Analysis at Patient Level -ITT Population
- Table 11.2. Summary of Secondary Endpoint Analysis at Patient Level -PP Population
- Table 12. Summary of Primary Endpoint Analysis by Reason for use of Scoreflex NC at Patient Level -ITT Population
- Table 13.1 Summary of Adverse Events -ITT Population
- Table 13.2 Summary of Relatedness of MACE to the Procedure and the Device -ITT Population
- Table 14.1 Baseline Angiographic Findings -ITT Population
- Table 14.2 Quantitative Angiographic Findings -ITT Population
- Table 14.3 Post Coronary Dilatation Catheter Morphology -ITT Population
- Table 14.4 Final Post-Procedure Morphology -ITT Population

14. DATA LISTINGS TO BE GENERATED

Listing 1. Demographics -ITT Population

Listing 2. Primary Safety and Efficacy Endpoint at Index Procedure -ITT Population

Listing 3. Secondary Endpoint -ITT Population

Listing 4.1 Angiographic Core Lab at Pre-Procedure -ITT Population

Listing 4.2 Angiographic Core Lab at Post-Scoreflex NC Coronary Dilation Catheter
-ITT Population

Listing 4.3 Angiographic Core Lab at Post Procedure -ITT Population

Listing 5. Medical History -ITT Population

15. FIGURES TO BE GENERATED

No Figures will be produced.
